## **Confidentiality**

Confidentiality will be maintained as follows: Data files are recorded with an identification number, are stored at the Center for Alcohol and Addiction Studies, and are accessed only by project staff. All project staff are knowledgeable about confidentiality and human subjects' protection. Follow-up contact forms that require identifying information are stored separately from data files and are accessed only by those staff conducting follow-up interviews. During follow-up telephone calls to the participants' homes, no information is provided to others in the household.

## Potential Research Risks / Discomforts to Participants

The following risks would need to be considered for this study -

- Legal risks (e.g., mandatory reporting).
  - a) Information would only be released to the appropriate authorities to the extent of the laws of Rhode Island.
- Psychological or emotional risks (e.g., fear, stress, confusion, guilt, loss of self-esteem, depression, triggering of past emotional experiences).
  - a. Potential Discomfort Relate to Questionnaires: Some questionnaires ask about sensitive information such as psychological and alcohol/drug problems. The questionnaires and interviews are commonly used in research and clinical practice; however, some questions may be of an embarrassing or sensitive nature. Some participants may experience discomfort in disclosing or discussing HIV status. To minimize this potential discomfort, questionnaires will be completed in a private study room. Also, a participant may refuse to answer or skip any question asked of him. They

do not have to answer any questions that they choose not to answer.

- b. Potential Discomfort in Quitting Smoking: Quitting smoking can result in uncomfortable withdrawal symptoms including mood changes, irritability, and changes in sleep. The nurse will discuss quitting smoking with each participant and will recommend actions they can take to reduce any symptoms related to nicotine withdrawal. The use of smoking cessation medications may also reduce these symptoms.
- Information risks (e.g., loss of privacy and/or breach of confidentiality)
  - a. Potential Breach of Confidentiality and/or Privacy: There is always a risk of loss of confidentiality. This risk will be minimized by conducting study interviews in a private room, assigning participants a study number and identifying this information only by this number, storing all study documents in a locked file cabinet in a locked office, and only using a password protected computer. Also, (if assigned to a peer navigator), it is important for a participant to know that the peer navigator is an employee of the clinic and is trained in maintaining confidentiality, similar to their doctor and nurse.

All of these risks are minimal and have a low magnitude effect. Currently MIC staff are HIPAA trained and they know confidentiality protocol after receiving extensive clinical training in order to work in this clinic setting.

In an effort to meet the NIH policy for Data and Safety Monitoring, we have created a system for oversight of the project. Oversight of internal monitoring of the participants' safety will be conducted by the PI, [name]. The internal Data Safety and Monitoring Board at the Center for Alcohol & Addiction Studies (CAAS) will participate in the oversight of this study. Investigators in the application have extensive experience with clinical trials for substance use disorders, tobacco dependence, and smoking cessation.

The PI and co-investigators will meet bi-weekly on the project, at which time they will evaluate the progress of the trial, review data quality, recruitment, and study retention, and examine other factors that may affect outcome. They will review the rates of adverse events to determine any changes in participant risk. A report will be generated semi-annually for the study record. It will also be forwarded to Brown University's Institutional Review Board. The Investigators will be available to meet outside of the weekly meetings, if necessary, due to concerns regarding a particular participant or any problems that may arise for participants. If necessary, they will make appropriate recommendations for changes in protocol. [name] will conduct daily oversight of participant safety. She will meet weekly with staff to review participant progress and their experience with the procedures, including adverse events. Any adverse events that are observed and/or reported will be immediately reported to [name]. Serious adverse events (SAEs) will be reported to the Brown University IRB immediately by telephone and by written report within 24 hours of our receipt of information regarding the event; SAEs will also be reported in writing to NCI. Adverse events will be reported to the Brown University IRBs and NCI semi-annually.

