#### **Enrollment**

Once the BL interview is complete, the PI, who is not involved in conducting assessments, will randomize eligible participants to one of two study conditions (PNSS-S or SC). The RA will not be informed of treatment condition assignment. All participants will be scheduled for a week 1 session with an MIC study nurse within one week of the BL appointment. The nurse will use a detailed counseling manual to ensure standardization of treatment delivery.

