#### Nurse Visit

All participants regardless of condition will meet with a MIC registered nurse at the clinic. The session will last for 30 minutes. See description of condition content in the following paragraphs.

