## Peer Navigation Social Support for Smoking Cessation Condition (PNSS-S)

Participants in the PNSS-S condition will also meet for a 30-minute session with the study nurse. The nurse will discuss the same content that was provided in the SC condition. In addition (for the PNSS-S condition participants only), the nurse will discuss the importance of social support for guitting and will explain the role of a Peer Navigator (PN). The nurse will then introduce the participant to his/her assigned PN. Finally, the nurse will ask if the participant is ready to set a quit date. Participants who set a quit date will choose the appropriate medication in collaboration with their clinic physician. PNs and nurses will reinforce adherence to the chosen medication. Participants will be informed of the efficacy of pharmacotherapy for smoking cessation. The PN will act as an intermediary between the patient and physician - facilitating the acquisition of the medication by coordinating with the participant's MD for a prescription, reviewing the formulary for medication coverage, ensuring that the prescription is picked up at the pharmacy, and managing any side effects via MD/nurse consultation (similar to their role in improving ART adherence). The PN will also assume the role of providing social support for quitting via weekly phone calls with the participant for 12 weeks. The PN will be well versed with local groups and resources, so that they can direct their participants to the most appropriate services/resources, if the participant is interested. Participants not willing to set a quit date at the time of the nurse visit will be engaged in a discussion of "quitting as a process" and will be encouraged to discuss barriers to quitting. This discussion will continue in contacts with the PN over the coming weeks.

In total, participants randomized to PNSS-S will receive a 30-minute session with the nurse, a quit-day counseling call from the PN (as appropriate), and weekly calls from the PN to address issues based on stage of quit attempt for 12 weeks.

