## Follow-up Visits (weeks 4, 12, and 24)

Participants will have vital signs checked. FEV1 will be assessed. Exhaled breath for carbon monoxide (CO) analysis will be obtained. Participants will then complete a series of paper/pencil assessments (See Attachments for Schedule of Assessments). A saliva sample will be obtained for cotinine analysis from any participant who reports that they have quit smoking (defined as no cigarette smoking for at least the past 24 hours).

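### The visible protocol describes no standard adverse-event question, and PNSS-S has about 16 scheduled contacts against 4 in SC, so SC events are likely to be under-counted and any by-arm tabulation would be hard to interpret

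*Combined protocol and SAP*

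**What the plan says.** The data and safety monitoring text, which follows Potential Research Risks / Discomforts to Participants, gives one capture rule: "Any adverse events that are observed and/or reported will be immediately reported to" a designated team member. Of the investigators it says: "They will review the rates of adverse events to determine any changes in participant risk". It also provides for weekly staff meetings that cover adverse events and for semi-annual reports to the IRB and NCI.

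Follow-up Visits (weeks 4, 12, and 24) begins "Participants will have vital signs checked. FEV1 will be assessed" and goes on to exhaled CO, questionnaires and, for those reporting that they have quit, saliva. Neither that section nor the descriptions of measures (Measures through Mechanisms of PNSS-S Effect) includes an adverse-event question, form or recall window. The Data Analysis Plan contains no adverse-event analysis.

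Both arms share the nurse session: "All participants regardless of condition will meet with a MIC registered nurse at the clinic". Only PNSS-S adds "weekly calls from the PN to address issues based on stage of quit attempt for 12 weeks", a quit-day call where relevant, and, under Recruitment Procedures, calls that participants may make to their PN during the first 12 weeks. The PN's tasks include "managing any side effects via MD/nurse consultation". SC participants who set a quit date are told to contact their physician for medication. No route is described by which their side effects would reach the study between visits.

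**The concern.** When an event is recorded only if someone notices it or the participant mentions it, the chance of recording depends on how often participants speak to staff and what they speak about. Here that opportunity differs by design, and the extra PNSS-S contact includes discussion of medication and side effects. SC participants may also be quitting and taking the same medications, but between the week 4 and week 12 visits they have no scheduled contact.

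Two things are at stake. The overall rates used to judge participant risk would be incomplete, with the shortfall mainly in SC. And if anyone later tabulates events by arm, for example when planning the full-scale trial, a PNSS-S excess could be dismissed as the product of more contact or accepted as real, with no data to tell which.

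**Working it through.** The plan gives no adverse-event rate, contact total or capture probability, so there is no stated figure to reproduce.

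**Step 1: scheduled contacts after randomisation.** Baseline is excluded because randomisation follows it (Enrollment: "Once the BL interview is complete, the PI, who is not involved in conducting assessments, will randomize eligible participants").

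| Contact | SC | PNSS-S |
|---|---|---|
| Nurse session (week 1) | 1 | 1 |
| Follow-up visits (weeks 4, 12, 24) | 3 | 3 |
| Weekly PN calls | 0 | 12 |
| **Total** | **4** | **16** (17 with a quit-day call) |

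- The ratio is 16/4 = 4.
- Through week 12, SC has 1 + 2 = 3 contacts and PNSS-S has 3 + 12 = 15.
- In weeks 13 to 24 each arm has one visit, so the imbalance lies entirely in the first 12 weeks.
- Intervals between scheduled SC contacts are 4 − 1 = 3, 12 − 4 = 8 and 24 − 12 = 12 weeks.

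**Step 2: what this could do to recorded rates.** The following is an illustration, and every input is an assumption. True rates are equal in the two arms and onset is uniform over 24 weeks. At each contact after onset, the event is reported with probability p × 0.5^(lag/h), where lag is weeks since onset and h is the recall half-life in weeks. An event is captured with probability 1 − Π[1 − p × 0.5^(lag/h)], the product running over all later contacts. SC contacts are at weeks 1, 4, 12 and 24; PNSS-S has these plus calls at weeks 1 to 12.

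| p | h (weeks) | Captured, SC | Captured, PNSS-S | Ratio |
|---|---|---|---|---|
| 1 | no decay | 1.000 | 1.000 | 1.00 |
| 1 | 4 | 0.542 | 0.710 | 1.31 |
| 0.5 | no decay | 0.648 | 0.740 | 1.14 |
| 0.5 | 4 | 0.287 | 0.557 | 1.94 |
| 0.25 | 4 | 0.147 | 0.389 | 2.64 |
| 0.10 | 1 | 0.021 | 0.082 | 3.98 |

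Ratios come from unrounded values. Over all settings tried (p from 0.10 to 1; h from 1 week to no decay) the range is 1.00 to 3.98. For onsets in weeks 0 to 12 alone it is 1.00 to 5.20.

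**Step 3: pooled review.** Pooling the arms does not remove the shortfall. With 36 per arm and p = 0.5, h = 4, the pooled capture is (0.287 + 0.557)/2 = 0.422. SC supplies 0.287/(0.287 + 0.557) = 34% of recorded events, although it has half of the true ones.

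**Step 4: effect of common elicitation.** If only events elicited at visits shared by both arms are counted, and reporting behaviour at those visits is the same, the ratio is 1.00 at any p and h by construction.

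**The case against.** A reader might infer three stronger claims, none of which the documents support.

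- *That the team will compare adverse-event rates by arm and be misled.* The monitoring text does not say the rates are split by arm, and neither the aims nor the analysis plan contains a safety endpoint. A misleading comparison is a risk only if someone makes one.
- *That rates will differ through ascertainment alone.* With complete recall the ratio is 1.00. PNSS-S is also meant to increase quit attempts and help participants obtain and adhere to medication, so withdrawal symptoms and side effects may truly differ. A recorded excess would be a mixture.
- *That the study has no adverse-event form.* The Schedule of Assessments, PN script and nurse counseling manual are not in the available text, and any of them might contain one.

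Other points also have force. Vital signs and FEV1 are checked equally in both arms. The SC nurse is to arrange follow-up, so 4 contacts may be a minimum. The study is a pilot of 72 randomised participants, using approved medications prescribed by participants' own physicians, and the protocol calls its risks minimal.

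These points limit the claim without removing it. Vital signs and FEV1 would not reveal the mood, irritability and sleep changes that the protocol itself lists as withdrawal effects. Pooled review still loses SC events. And if true rates do differ, common elicitation becomes more useful, because without it the two causes cannot be separated.

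**Conclusion.** The point holds as a weakness in the described capture of adverse events. It does not show that a planned comparison is wrong. The contact imbalance, 16 against 4 overall and 15 against 3 through week 12, follows directly from the protocol, as does the absence of a standard question from the visible text. SC events are therefore likely to be under-counted in the reviewed and reported rates, and a by-arm table would combine unequal capture with any real difference.

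The direction, more recorded events in PNSS-S, rests on equal true rates and imperfect spontaneous reporting. The size cannot be fixed from the documents: the 1.00 to 3.98 range reflects assumed inputs only. If an attachment already holds a common adverse-event form used in both arms, the gap is one of cross-reference only. The change is worth making because it is cheap.

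**What to change.** Check the attachments first. If one already provides a common adverse-event form, cite it under Follow-up Visits and in the monitoring text. Otherwise:

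1. Have the RA ask every participant in both arms the same short adverse-event question set at weeks 4, 12 and 24, covering events since the last study visit (since baseline at week 4), with dates.
2. Record the source of each event (study visit, PN call, nurse, spontaneous) on a log the RA does not see, kept by someone who already knows assignment. The RA is not told the condition, and a PN entry would reveal it.
3. Base any by-arm rate only on events elicited at these shared visits.
4. Keep reporting all events for safety, with PN-sourced events tabulated separately.

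The cost is one page at three existing visits, a few minutes each, and one extra log field. The by-arm rates would rest on recall over up to 12 weeks. Some bias would remain, because weekly discussion with a PN may itself improve recall at the visits. No treatment procedure changes.

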## **Compensation / Reimbursement**

Total possible compensation is \$180, according to the following schedule: \$40 for the BL assessment; \$25 for the nurse visit; \$25 for the week 4 assessment, \$40 for the week 12 assessment; and \$50 for the week 24 assessment. Participants will receive compensation only for the sessions they complete, and compensation will not be contingent upon smoking status. If a participant is ineligible at Baseline, they will be compensated \$10 for their time. This amount is similar to payments made by similar, previous studies. The amount helps to cover transportation costs and compensates the participants for the time spent with the research staff at the visit.

#### Data Analysis Plan

Assessments will be designed as scannable forms for use with the Cardiff Teleform Scanner System®. Data will be verified, checked, and uploaded to an SPSS file to conduct analyses. Initial data analysis will include studies of randomization effects (group differences), distribution properties of dependent and other variables, and correlations among outcome measures.

Sample Size and Power Considerations. Our primary objective will be to examine preliminary effect sizes for PNSS-S, rather than to determine statistical significance between groups at certain p values. At the same time, we are well aware of the dangers of relying exclusively on small-scale pilots to determine the promise of novel treatment approaches. These effect size estimates have a large standard error, and we primarily will be hoping to find a pattern of results that is supportive of the experimental treatment. Effect size estimates will include odds ratios for smoking abstinence. We believe a sample size of 72 should allow adequate examination of PNSS-S intervention effect sizes while staying within the scope of a developmental project. We recognize that only medium to large effect sizes will be likely to attain statistical significance with a sample of this size. Our data also will allow us to obtain stability estimates for point-prevalence abstinence (i.e., intercorrelations among outcomes at 4, 12, and 24 weeks). Using a program that allows us to specify proportions at each time point and the correlations between time points, we will be able to get a good estimate of the sample size needed to find a significant main effect of treatment in a repeated measures analysis using generalized estimating equations. All analyses will include sex as a covariate and follow-up analyses will test the Sex x Condition interaction to determine whether sex moderates the effects.

Treatment Feasibility, Acceptability, & Efficacy. Individual analyses of variance will be conducted to compare treatments (PNSS-S vs. SC) on the continuous variables of number of sessions attended and client satisfaction scores. For treatment retention rate (dichotomous), a chi-square analysis will be used. Analyses will test the hypothesis that PNSS-S improves point prevalence abstinence relative to SC. Tests of the effect of treatment condition on Quitline usage, quit attempts, and on 7-day point-prevalence abstinence across the 4, 12, and 24 week assessments will be conducted using GEE, which provides appropriate modeling of covariance structures when observations are correlated across time. The primary, between groups, independent variable in the GEE analysis is treatment condition assignment, which will be dummy-coded using SC as the reference group.

Following the intention-to-treat principle, all participants who have been randomized will be included in the analyses.

Potential Mechanisms of PNSS-S Effects. Sample size in this trial precludes formal mediation analysis with adequate power. The analyses are designed to test the plausibility of potential mechanisms of the PNSS-S treatment effect. We will examine change in these variables using multilevel modeling as increased social support and self-efficacy for quitting are important outcomes in and of themselves, which may affect long-term smoking outcomes and will be useful in demonstrating the longer-term effects of PNSS-S. Mediators will be examined separately, rather than simultaneously, given our limited sample size. For each mediator, we will fit a multilevel model to obtain both an initial value (intercept) and rate of change (slope) in each of these variables from baseline to week 4. We will first test whether treatment condition predicts change in these variables. We will then enter the intercept and slope parameters from these models into the main GEE model of smoking outcome to determine whether change in these variables predicts smoking outcomes. We will be able to examine whether the effect of treatment is reduced when the mediator is added to the model and can test for significance (not expected given the sample size) using the products of coefficients method. Social support in the 4 weeks after quitting also will be examined as a potential mediator of PNSS-S effects.

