The primary objective of this project is to examine the feasibility, acceptability and initial efficacy of a peer navigation social support for smoking cessation (PNSS-S) intervention for HIV-positive smokers. We will enroll 78 HIV-positive smokers, regardless of their readiness to quit, into a 24-week randomized pilot study to determine whether enhanced treatment (using a PN to navigate smoking cessation, help obtain medication and treatment, improve adherence to treatment, and provide social support for quitting) will increase quit attempts and smoking cessation rates (measured by 7-day point prevalence) compared with standard care (SC; provider recommendation to quit and quit line referral using the 5A's).

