## **Baseline Measures of Individual Differences**

Demographics will include age, sex, gender, race, ethnicity, marital status, employment status, income, education level, number of years living with HIV, and history of opportunistic infections. We will obtain most recent CD4 T-cell value and HIV viral load from the MIC medical record (commonly measured in the clinic every 3-6 months). The Fagerström Test for Cigarette Dependence (FTCD) will be administered to evaluate severity of cigarette dependence. An exhaled carbon monoxide (CO) level will be obtained (using a Smokerlyzer ED50 CO meter [Bedfont Scientific, Haddonfield, NJ]), a valid assessment of recent smoking. Participants will provide breath samples for CO at baseline, and each study interview; values of 5 ppm or higher will be considered indicative of smoking. Intention to quit smoking will be assessed using the Smoking Stage of Change questionnaire. Depressive symptoms will be assessed with the Center for Epidemiologic Studies –Depression scale (CES-D).

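### Should the efficacy GEE also adjust for baseline readiness to quit, since smokers are enrolled at every level of readiness?

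*Combined protocol and SAP*

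**What the plan says.** The section on the purpose of the project opens enrolment at every level of readiness: "We will enroll 78 HIV-positive smokers, regardless of their readiness to quit, into a 24-week randomized pilot study". The Methodology and Participant Population sections split the 78 into 6 who test the intervention and 72 who are randomised, 36 per arm.

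Readiness is known before allocation. Under Baseline Measures of Individual Differences, "Intention to quit smoking will be assessed using the Smoking Stage of Change questionnaire", and under Enrollment, "Once the BL interview is complete, the PI, who is not involved in conducting assessments, will randomize eligible participants". No stratification is described. Other possible predictors are collected at the same visit: the Fagerström test "will be administered to evaluate severity of cigarette dependence", and the CES-D measures depressive symptoms.

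For the analysis, the Data Analysis Plan states "All analyses will include sex as a covariate". The efficacy paragraph adds treatment condition, with standard care as reference, across weeks 4, 12 and 24. Mediator intercepts and slopes enter the GEE only in the separate mechanism analysis. The aim is to examine preliminary effect sizes "rather than to determine statistical significance between groups at certain p values", and "Effect size estimates will include odds ratios for smoking abstinence".

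**The concern.** A baseline variable that predicts the outcome can sharpen a randomised comparison, at no data-collection cost if it is already recorded. Readiness is a natural candidate. Enrolment leaves it free to vary, and both arms' nurse visits branch on whether the participant will set a quit date. With only 36 per arm, chance imbalance in readiness is likely, and the plan itself admits that its estimates will have large standard errors. If readiness were strongly prognostic, a model with sex alone would give up precision in a trial whose product is an effect estimate. The plan also examines baseline group differences without saying whether these may change the model, which could be read as leaving room for covariates chosen after the fact.

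**Working it through.** **1. Validity.** Readiness is measured before randomisation, so allocation is independent of it. The unadjusted comparison is unbiased on average, and its standard error already includes chance imbalance. Only efficiency is left to examine.

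**2. Inputs.** From the documents: 72 randomised, 36 per arm, three visits, abstinence as a binary outcome. The documents give no abstinence rate, share ready or prognostic strength. Assumed: 13% control abstinence (72 × 0.13 = 9.4 abstainers per visit with no treatment effect), 40% ready unless stated, and readiness odds ratios (OR) from 1 to 6.3.

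**3. How much variance can readiness explain?** With share ready q and stratum rates p1 (ready) and p0 (not ready), the explained share of outcome variance at one visit is q(1−q)(p1−p0)² / [p(1−p)], where p(1−p) = 0.13 × 0.87 = 0.1131.
- OR 3, 40% ready: rates 20.6% and 7.9%; 0.24 × 0.127² / 0.1131 = 3.4%.
- OR 3, 80% ready: rates 14.9% and 5.5%; 0.16 × 0.094² / 0.1131 = 1.2%.
- OR 6.3, 40% ready: rates 25% and 5%; 0.24 × 0.20² / 0.1131 = 8.5%.

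A person's visits are correlated, so the three-visit figure differs somewhat. The extra parameter also costs 1-2%.

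**4. Three-visit simulation.** Logistic GEE with arm, sex and visit, with and without one binary readiness term; independence working correlation; latent correlation 0.7 between visits; 6,000 trials per scenario. Change in the variance of the standardised risk difference:

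| Assumption about readiness | Change |
|---|---|
| OR 1, 40% ready | +1.2% |
| OR 2, 40% ready | −0.6% |
| OR 3, 40% ready | −3.2% |
| OR 3, 80% ready | −0.4% |
| OR fading 3, 2, 1.5 over the visits, 40% ready | −0.6% |
| OR 3 in both arms, treatment OR 3 | −5.7% |
| As the row above, but a weaker readiness OR in PNSS-S | −1.6% |

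The third row is worth 72 / 0.968 = 74.4 participants, about two more than 72. It shortens the standard error by 1.6% (√0.968 = 0.984).

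**5. The measure the plan names.** At readiness OR 3 with no treatment effect, the 95% range of the estimated odds ratio is 0.29-3.37 without readiness and 0.28-3.53 with it. On the log scale the width goes from ln(3.37/0.29) = 2.45 to ln(3.53/0.28) = 2.53, about 3% wider. Its meaning also changes, because it becomes conditional on readiness. A run of 20,000 trials gave 0.29-3.47 and 0.28-3.62, again 3% wider. Converting the adjusted result back to a marginal odds ratio gave 0.30-3.34, about 3% narrower, but the plan names no such standardised quantity.

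**6. Power.** With a small-sample-corrected (Mancl-DeRouen) standard error and a conditional treatment OR of 3, power without and with readiness is 0.612 and 0.599 at readiness OR 1, 0.581 and 0.578 at OR 2, 0.549 and 0.565 at OR 3, and 0.461 and 0.515 at OR 6.3.

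**7. Sizing the next trial.** The plan sizes it from proportions: "Using a program that allows us to specify proportions at each time point and the correlations between time points". A conditional odds ratio would be a worse input. Applied to 13%, an OR of 3 gives 30.95%. The pooled two-proportion formula (two-sided 0.05, power 0.80) then asks for 83 per arm. If readiness has OR 3 and 40% are ready, the true treated proportion is 29.84% and 92 per arm are needed.

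**The case for a change.** The best case for adjustment is that the plan's own yardstick is precision, that the future trial will be sized from proportions, and that the risk difference is where adjustment helps. If readiness is very strongly prognostic the gain is real: at OR 6.3, with 20% or 40% ready, the variance falls by 9.6 to 15.8%. The change would need wording only, and would be credible only if fixed before outcomes are seen.

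This is correct as far as it goes, but it depends on a figure the documents do not supply. Nor do they rank readiness above cigarette dependence or depressive symptoms. A fixed OR of 3 is not sufficient for a useful gain either, as the rows for fading, arm-dependent and majority-ready readiness show. A majority-ready sample is plausible: the project description says most HIV-positive smokers strongly want to quit, and participants volunteer by answering flyers. PNSS-S also works on those not yet ready, so a weaker association in that arm is plausible too.

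The term also has costs. With about 9 abstainers per visit, one more parameter strains the fit. In simulations at 5% versus 15% abstinence with readiness OR 10, non-convergence or separation rose from about 2% to 9%. A sound version would need a corrected standard error, a fallback model and several estimates reported together.

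One small point stands: the plan does not say that the baseline group comparison is purely descriptive. That is missing detail. Nothing in the text lets that comparison add covariates.

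**Conclusion.** The concern does not hold. Sex is indeed the only covariate named for the efficacy GEE, but that is a legitimate, parsimonious choice for a 72-person pilot seeking preliminary effect sizes. It causes no bias and does not invalidate any standard error. At 13% abstinence and 40% ready, with no treatment effect, the precision at stake runs from a loss of about 1% in risk-difference variance (readiness OR 1) to a gain of about 3% (OR 3). With a treatment OR of 3 and a common readiness OR of 3, the gain is about 6%. It shrinks to between 0.4% and 1.6% if most participants are ready, if the association fades, or if it is weaker in PNSS-S. Larger gains need odds ratios well above 3, which nothing in the documents supports or excludes. The plan's named measure, the odds ratio, is not estimated more tightly. All rates, shares and prognostic strengths here are assumptions. Whether to add readiness is a matter of preference, and no change to the plan is called for.
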